4.5 Datasets to be Analyzed

All patients fulfilling all inclusion criteria and none of the exclusion criteria will be evaluated in an Enrolled Set.

Inclusion criteria are:

- diagnosis with T2DM,
- ≥ 18 years of age at index date,
- initiation of EMPAGLIFLOZIN or DPP-4 inhibitor treatment according to the local label and at the discretion of the treating physician,
- signed informed consent form.

Exclusion criteria are:

- use of SGLT2 inhibitors during the previous 12 months,
- known hypersensitivity to EMPAGLIFLOZIN, the comparator DPP-4 inhibitors or any of their excipients,
- contraindication of EMPAGLIFLOZIN or the comparator DPP-4 inhibitor according SFDA approved label, and
- prescribed fixed-dose combination of SGLT2 inhibitors with DPP-4 inhibitors.

The propensity score analysis will lead to the creation of a Matched Set comprising a subset of subjects in the Enrolled Set (see section 4.9.3). This dataset will be used for additional analysis.

Frequencies of patients included in and excluded from analysis sets will be given.

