Study design:	
This will be non-interventional study with new data collection. The study will use a “new users” design and compare new users of Jardiance® (Empagliflozin) to new users of DPP-4 inhibitors. The index date will be defined as the date on which each identified new user receives the index prescription for Jardiance® (Empagliflozin) or a DPP-4 inhibitor.
 
Number of recruited patients will be comparable in each group within a given timeframe (i.e. each site will ensure to recruit similar number of patients for each group according to assigned blocks of enrolment)
 
Propensity scores based on information prior to the index date will be used to account for potential confounding.
 
Patients will be follow-up for 12 months after index date.
		
Population:	
Patients diagnosed with T2DM in Saudi Arabia
 
The study population will include patients aged at least 18 years and diagnosed with T2DM in Saudi Arabia and who will initiate Jardiance® (Empagliflozin) treatment during the study period and who have not used other SGLT2 inhibitors during the previous 12 months.
 
Patients switching to or adding Jardiance® (Empagliflozin) to other antidiabetic medications will be compared to patients switching to or adding comparator treatment on same background therapy. This modification of a “new-user” design is an appropriate method for studying second-line therapies in chronic conditions.
 
The comparator groups will include new users of DPP-4 inhibitors. The same inclusion and exclusion criteria will be applied.
 
  Patients with a confirmed diagnosis of type 1 diabetes before or after the index date will not be included in the study.  Patients prescribed fixed-dose combinations of SGLT2 inhibitors with DPP-4 inhibitors will be excluded. 		

Name of company: [REDACTED]			
Name of finished medicinal product: Jardiance®			
Name of active ingredient: Empagliflozin			
Protocol date: 16 Oct 2017	Study number: 1245.149	Version/Revision: 3.0	Version/Revision date: 23 Sep 2019

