9. RESEARCH METHODS

This is a non-interventional study with new data collection.

This study will cover the period between Q3 2018 and Q4 2020. The main goals of this study are to examine the risk of ketoacidosis, severe urinary tract infections, volume depletion, and dehydration associated with the use of Empagliflozin compared to the use of DPP-4 inhibitors in T2DM patients. The study will use an “incident users” design and compare new users of Empagliflozin with new users of DPP-4 inhibitors. The index date will be defined as the date on which each identified new user receives the index prescription for Empagliflozin or DPP-4 inhibitors. The definition of drug exposure for Empagliflozin will be any patient using at least one prescription of Empagliflozin tablets (10 or 25 mg) or fixed-dose combinations with metformin. The comparator group will be comprised of patients with at least one prescription of a DPP-4 inhibitor: sitagliptin, saxagliptin, linagliptin, vildagliptin, alogliptin (and fixed-dose combinations of these drugs with metformin). Each member of the population exposed to Empagliflozin must have at least one prescription for Empagliflozin, with or without other Glucose-lowering Drugs (GLDs,) and no prior prescriptions of a DPP-4 inhibitor or Empagliflozin during the available pre-index period. Each member of the population exposed to a DPP-4 inhibitor must have at least one prescription for a DPP-4 inhibitor, with or without other GLDs, and no prior prescriptions of a DPP-4 inhibitor or Empagliflozin during the available pre-index period.

Follow-up will start the day after the index date and will continue until any of the following conditions are met: date of death or after 12 months of follow-up, or the date during follow-up that specific exclusion criteria are met, the date of the last continuous treatment of the index drug (Empagliflozin or DPP-4 inhibitor) plus a defined grace period (30 days after the end of the last prescription’s days’ supply in main analyses), or the date in which a new treatment episode starts with any of the other index drugs. Patients who discontinue an index drug and then subsequently initiate another index drug will not be allowed to re-enter the study. Patients will be followed-up for 12 months.

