9.2.2 Study population

Main diagnosis for study entry

- Patients diagnosed with T2DM will be included.

[figure not shown]
Inclusion criteria:

- Patients who have signed Informed consent form.
- The patients will be at least 18 years old at index date, diagnosed with T2DM in Saudi Arabia, and who will initiate Empagliflozin or DPP4 inhibitors treatment according to the local label and at the discretion of the treating physician during the study period, who have not used other SGLT2 or DPP4 inhibitors during the previous 12 months.

Exclusion criteria:

- Known hypersensitivity to Empagliflozin, the comparator DPP-4 inhibitors or any of their excipients
- Patients for whom Empagliflozin or the comparator DPP-4 inhibitor is contraindicated according SFDA approved label
- Patients prescribed fixed-dose combinations of SGLT2 inhibitors with DPP-4 inhibitors will be excluded.
- The same inclusion and exclusion criteria will be applied to the comparator group, which will include new users of DPP-4 inhibitors.

- **Study visits**

* From Visit 1

Figure 2: Study Visits

Baseline Visit

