9.3.2 Exposures

The definition of drug exposure for Empagliflozin will be any patient using at least one prescription of Empagliflozin tablets (10 or 25 mg) or fixed-dose combinations with metformin. For the comparator group, the patients will have at least one prescription of DPP-4 inhibitors. DPP-4 inhibitor users included in this study will be using one of the following approved drugs in Saudi Arabia: Sitagliptin, Saxagliptin, Vildagliptin, Alogliptin, Linagliptin, or fixed-dose combinations of these drugs with metformin. [R17-3427]

Furthermore, each member of the population exposed to Empagliflozin must have at least one prescription for Empagliflozin, with or without other glucose-lowering drugs (GLDs), and have no prior prescriptions of a DPP-4 inhibitor or Empagliflozin during the available pre-index period. Each member of the population exposed to a DPP-4 inhibitor must have at least one prescription for a DPP-4 inhibitor, with or without other GLDs, and no prior prescriptions of a DPP-4 inhibitor or Empagliflozin during the available pre-index period.

Add-on therapy will be allowed after using the exposure of interest as the initial drug for new users. Therefore, using the drug as part of dual therapy or triple therapy will be allowed.

The use of studied medications will be defined on different levels: current use, recent use and discontinuation of the studied drugs. Current use of the index drugs will be defined from the date of prescription of Empagliflozin or DPP-4 inhibitor to the end of supply for that prescription plus a period of 30 days. Recent use will be defined from the end of current use (30 days after end of supply) until 90 days later (which is 120 days after end of supply).

Discontinuation of the index drug will be defined as no further prescription 120 or more days after the end of the last prescription's supply. Patients who discontinue an index drug and then subsequently initiate another index drug will not be allowed to re-enter the study.

Patients switching to or adding Empagliflozin to other antidiabetic medications will be compared to patients switching to or adding comparator treatment on the same background therapy. Identification of a "new-user" design is an appropriate method for studying second-line therapies in chronic conditions.

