3 STUDY OVERVIEW

The study will use an “incident users” design and compare new users of EMPAGLIFLOZIN with new users of DPP-4 inhibitors.

This study will be carried out by conducting successive surveys over the follow-up period. The investigator will be asked to record the information from the surveys in the case report forms

Statistical Analysis Plan (SAP)

Document Date: 17APR2019

Document Version: 1.0 Final

(e-CRFs) from each subject who was initially administered the drug following the study start date until the requested number of subjects is reached.

The index date for each identified new user is defined as the date on which they receive the index prescription for EMPAGLIFLOZIN or DPP-4 inhibitors.

Patients are enrolled if at least 18 years of age at the index date, diagnosed with T2DM in Saudi Arabia, and who have not used other SGLT2 inhibitors during the previous 12 months. Patients are not enrolled if they have known hypersensitivity to EMPAGLIFLOZIN, the comparator DPP-4 inhibitors or any of their excipients, if EMPAGLIFLOZIN or the comparator DPP-4 inhibitor is contraindicated according SFDA approved label, or if they are on prescribed fixed-dose combinations of SGLT2 inhibitors with DPP-4 inhibitors.

Follow-up will start the day after the index date and will continue until any of the following conditions are met:

- Death
- 12 months of follow-up
- specific exclusion criteria are met during follow-up
- the last continuous treatment of the index drug (EMPAGLIFLOZIN or DPP-4 inhibitor) plus a defined grace period (30 days after the end of the last prescription's days' supply in main analyses)
- a new treatment episode starts with any of the other index drugs.

Patients who discontinue an index drug and then subsequently initiate another index drug will not be allowed to re-enter the study.

Four study visits will be held, at baseline, after 16, 32 and 52 weeks of follow-up.

[figure not shown]
[REDACTED]

Statistical Analysis Plan (SAP)

Document Date: 17APR2019

Document Version: 1.0 Final

Figure 3-1: Study Visits

* from Visit 1

Table 3-1: Schedule of Visits

Assessment	Visit 1	Visit 2	Visit 3	Visit 4
Informed Consent	X			
Demographics	X			
Diagnosis	X			
Medical History	X			
HbA1c	X	*	*	*
Blood glucose level	*			
Other Laboratory/Renal Function	*			
Physical Examination (for vital signs)	X	*	*	*
Concomitant Medication incl. anti-hyperglycemic	X	#	#	#
Dose of Empagliflozin / DPP-4 inhibitor	X	#	#	#
Adverse Events		X	X	X

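### The SAP's Enrolled Set excludes prior SGLT2 inhibitor use only, while protocol 9, 9.2.2 and 9.3.2 also bar prior DPP-4 inhibitor use in both cohorts

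*SAP*

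**What the plan says.** SAP 4.5 admits to the Enrolled Set every patient who meets all of its listed inclusion criteria and none of its listed exclusions. The only exclusion about earlier treatment is "use of SGLT2 inhibitors during the previous 12 months". The nearest text on new use of a DPP-4 inhibitor is the inclusion criterion "initiation of EMPAGLIFLOZIN or DPP-4 inhibitor treatment according to the local label and at the discretion of the treating physician". SAP 3 describes enrolled patients as those diagnosed with type 2 diabetes "and who have not used other SGLT2 inhibitors during the previous 12 months". SAP 1 and SAP 3 call the comparison one between new or incident users.

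The protocol words the restriction in three ways:

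- Abstract, Population: "who have not used other SGLT2 inhibitors during the previous 12 months".
- Section 9.2.2, inclusion criteria: "who have not used other SGLT2 or DPP4 inhibitors during the previous 12 months".
- Section 9, for each cohort: "no prior prescriptions of a DPP-4 inhibitor or Empagliflozin during the available pre-index period". Section 9.3.2 repeats this: patients must "have no prior prescriptions of a DPP-4 inhibitor or Empagliflozin during the available pre-index period". Neither section gives the length of that period.

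SAP 4.5 also promises a count: "Frequencies of patients included in and excluded from analysis sets will be given". Table 1 of the planned outputs covers the analysis sets.

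**The concern.** New use is the design's main stated protection. Protocol 9.1 and SAP 4.1 both justify it as a way to avoid comparing first-time users with people already established on an older drug. An analysis-set rule should turn that definition into a filter and catch patients enrolled in error. This filter cannot catch a breach of the DPP-4 criterion, because DPP-4 inhibitors are not in it.

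Two kinds of patient could pass. One took a DPP-4 inhibitor recently and then switched to empagliflozin or added it. That patient does initiate empagliflozin, and the protocol expects switching and adding on as routes of entry. The other restarted a DPP-4 inhibitor, or changed from one to another. Protocol 9, 9.2.2 and 9.3.2 make the recent users among both ineligible, but SAP 4.5 does not. The study report could then describe a cohort restriction that the analysis had not applied.

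**Working it through.** The plan gives no figure on this point, so there is none to reproduce. The check is a comparison of texts, followed by a scale calculation on assumed inputs.

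**1. The texts side by side**

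| Place | Prior SGLT2 inhibitor | Prior DPP-4 inhibitor | Look-back |
|---|---|---|---|
| SAP 4.5 (defines the Enrolled Set) | barred | not mentioned | 12 months |
| SAP 3 | other SGLT2 inhibitors barred | not mentioned | 12 months |
| Protocol abstract | other SGLT2 inhibitors barred | not mentioned | 12 months |
| Protocol 9.2.2 | other SGLT2 inhibitors barred | barred | 12 months |
| Protocol 9 and 9.3.2, both cohorts | empagliflozin barred | barred | whatever pre-index period is available |

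The SAP thus follows one of the protocol's own versions, the abstract's, and departs from three sections of its body. Protocol 9 and 9.3.2 also differ from 9.2.2 in drug coverage and look-back.

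**2. Document version.** The SAP is dated 17 April 2019, before protocol 3.0 of 23 September 2019. The amendment log gives only milestone changes for versions 2.0 and 3.0, so it offers no sign that the criterion changed between versions.

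**3. Adjustment instead of exclusion.** Protocol 9.3.4 lists the five DPP-4 inhibitors among prior drugs (items 72 to 76) and allows listed variables to be considered for the propensity model. The prior-drug list in SAP 4.9 is open-ended but does not name DPP-4 inhibitors. Adjustment is possible but not specified.

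**4. Scale.** Let pE and pD be the shares of person-time from prior DPP-4 users in the empagliflozin and DPP-4 cohorts, and r their event rate relative to true new users. Each cohort's rate is then multiplied by 1 − p(1 − r), so

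IRR factor = [1 − pE(1 − r)] / [1 − pD(1 − r)].

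All three inputs are assumptions. With 750 planned per cohort, 1% is 750 × 0.01 = 7.5 patients and 5% is 750 × 0.05 = 37.5, or about 8 to 38.

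| Prior users only in | r | 1% share | 5% share |
|---|---|---|---|
| DPP-4 cohort | 0.5 | 1/0.995 = 1.005 | 1/0.975 = 1.026 |
| DPP-4 cohort | 1.5 | 1/1.005 = 0.995 | 1/1.025 = 0.976 |
| Empagliflozin cohort | 0.5 | 0.995 | 0.975 |
| Empagliflozin cohort | 1.5 | 1.005 | 1.025 |

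If r = 1, or if pE = pD, the factor is 1.00.

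For comparison, with e events per cohort and equal person-time, the 95% limits of a crude IRR lie a factor exp(1.96 × √(2/e)) either side of the estimate. For an assumed e of 5, 10 and 20 this is 3.45, 2.40 and 1.86.

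**The case against.** The strongest reply is that sites enrol under protocol 9.2.2, which already bars prior DPP-4 use. The SAP gap then touches only protocol violators, or patients enrolled on the abstract's wording. This stands, and it is why the expected effect is small. It does not make the filter right, since removing ineligible patients is part of what the filter is for.

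A second reply is that SAP 1, 3 and 4.5 speak of new use, incident users and initiation. These words state the intent and may remove someone merely continuing a DPP-4 inhibitor. They set no look-back and do not reach a recent DPP-4 user who starts empagliflozin.

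A third is that planned outputs already show much of this. SAP 4.7.2 summarises antihyperglycaemic drugs used in the previous six months by group. The prior-medication definition in SAP 4.7.6, unlike its concomitant-medication definition, does not leave out DPP-4 inhibitors. Table 5.1 and Listings 7 and 13.1 report prior drugs and eligibility. This also stands: recorded prior use within six months should be visible. It would still not be removed from the primary analysis.

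A reader might go further and infer that the primary comparison is contaminated by established users and biased in a known direction. The documents do not support that. Protocol 9.1 and SAP 4.1 say that long-staying users may be less susceptible to the events, but a patient who stopped or changed a DPP-4 inhibitor has not clearly stayed on it. Protocol 9.9 notes treatment changes due to advancing diabetes or adverse effects, which could act the other way.

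**Conclusion.** The mismatch is real and should be corrected. The rule as written for the Enrolled Set does not deliver the population that protocol 9, 9.2.2 and 9.3.2 define, and the protocol disagrees with itself on the same criterion.

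The numerical stake is small. The number of patients affected is unknown and may be near zero. With a share of 1% to 5% in one cohort and a relative event rate of 0.5 to 1.5, the IRR shifts by at most about 2.6% in either direction, well inside sampling error at the assumed event counts. The case rests on the analysis set matching the protocol and on any violators being counted.

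One reservation: SAP 4.10, on changes from the protocol, is partly redacted, and section 4.9.3 is not visible in the public text. The visible text declares no eligibility change, but a declared one cannot be ruled out.

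**What to change.** 1. Reconcile the prior-use criterion across protocol 4, 9, 9.2.2 and 9.3.2: which drugs it covers, and whether the look-back is 12 months or the available pre-index period.
2. Make the exclusion in SAP 3 and 4.5 match the reconciled criterion, so that it covers prior DPP-4 inhibitor as well as SGLT2 inhibitor use.
3. Apply it from the Visit 1 eligibility entry (protocol 9.2.2.1, SAP Listing 7) and the prior-drug data already planned (protocol 9.2.2.1, 9.3.4 and 9.4; SAP 4.7.2 and 4.7.6, Table 5.1, Listing 13.1).
4. Report the number excluded for this reason, per cohort, in Table 1. A count of zero is also worth reporting.
5. State the limit of the data. Protocol 9.2.2.1 and 9.3.4 record prior antihyperglycaemic drugs for six months only, so any longer look-back rests on the eligibility entry or the medical record.

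Repeating the primary analysis with the excluded patients put back is optional; at the sizes above it is unlikely to be informative.

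The cost is a wording clarification in the protocol, a line in each of two SAP sections, one filter and one table row. No new data collection is needed. The downside is that any violators leave the primary set, and that use more than six months before baseline may be unverified for some patients.

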4.5.1 Groups and subgroups

Patients are grouped according to the exposure to either EMPAGLIFLOZIN or DPP-4 inhibitors. Data will be analysed per group. DPP-4 inhibitors used include sitagliptin, saxagliptin, linagliptin, vildagliptin, and alogliptin.

Statistical Analysis Plan (SAP)

Document Date: 17APR2019

Document Version: 1.0 Final

All tables will show results per group (EMPAGLIFLOZIN or DPP-4 inhibitors) and for all patients in the analysis set. Additionally, selected tables will show results in subgroups for patients according to their metformin status, namely, whether or not they use metformin fixed combination therapy. Further subgroups are defined by mono, dual or triple therapy with glucose-lowering drugs (GLD) (the treatment complexity status), and by insulin use at baseline (the insulin status).

4.6 Statistical Hypotheses

If not otherwise specified, the level of significance is set to 0.05. All statistical tests will compare the treatment groups, EMPAGLIFLOZIN versus DPP-4 inhibitors, for difference. The null hypothesis is of no difference versus the two-sided alternative hypothesis which hypothesizes a difference between groups.

4.7 Analysis Parameters

All collected and derived individual data will be listed. Any derivations are described below. Parameter definitions are given. Summary tables and figures will be presented for the following data modules in all patients of the Enrolled Set. Analysis details are given below. On selected analysis parameters, summary tables and figures will also be prepared for the Matched Set.

4.7.1 Diagnosis and Family History of T2DM

The duration of T2DM will be determined as the time from date of diagnosis to index date in months.

Details of diagnosis will be listed and described per group by means of summary tables.

Details of diagnosis include

- Duration of disease in months, as the time from date of diagnosis to index date, calculated as the time span in days divided by 365.25/12,
- T2DM-related complication (retinopathy, neuropathy, nephropathy)
- Family history of T2DM. (yes/no)
- Insulin use (yes/no)
- HbA1c
- Fasting blood glucose level
- Treatment complexity (single,dual,triple)

Statistical Analysis Plan (SAP)

Document Date: 17APR2019

Document Version: 1.0 Final

4.7.2 Demographic and Other Characteristics

Demographic and other baseline characteristics will be listed and described per group by means of summary tables.

Demographic and other baseline characteristics include

- Gender,
- Age at index date in years, as the time from date of birth to index date,
- Age category (<30 years, 30 to 64 years and >64 years),
- Medical history (see below),
- Baseline laboratory test results, if available: complete blood count, oral glucose tolerance test, ketones level, amylase, lipase, arterial blood gas, pH, bicarbonate, lipid profile tests, blood urea nitrogen, liver tests, International Normalized Ratio (INR) for prothrombin time,
- Renal function (within the last two months): Serum creatinine, eGFR, urine ACR,
- Physical examination at baseline: sBP (mmHg), dBP (mmHg), pulse rate (beats/min), weight (kg), height (cm), BMI (kg/m²),
- Previous (within six months) and concomitant use of anti-hyperglycaemic agents at baseline,
- Previous (within one month) and concomitant medication at baseline.

Relevant medical history will be captured along with the start and end date of any condition and its status at enrollment (ongoing versus not ongoing). The medical history terms will be coded using the MedDRA dictionary, version 21.1. A table presenting the number and percentage of patients reporting medical history with respect to the system organ class (SOC) and preferred terms will be presented. Another such table will present the same for the subset of concomitant diseases ongoing at enrollment, i.e., at index date.

4.7.3 Exposure

Patients either receive EMPAGLIFLOZIN or a DPP-4 inhibitor, they may or may not receive respective fixed combinations with metformin and they may or may not combine the treatment with other GLDs.

To describe exposure, the following parameters will be derived:

- Duration of treatment as the length of the index period in days
- Number of interruptions of EMPAGLIFLOZIN or a DPP-4 inhibitor intake

Statistical Analysis Plan (SAP)

Document Date: 17APR2019

Document Version: 1.0 Final

- Extent of exposure as duration of treatment minus the number of days with interruptions
- Initial dose of EMPAGLIFLOZIN or a DPP-4 inhibitor
- Final dose of EMPAGLIFLOZIN or a DPP-4 inhibitor
- Proportion of subjects on metformin fixed-combination
- Proportion of subjects on mono, dual or triple therapy with other GLDs
- Proportion of subjects with insulin intake
- Proportion of subjects still on EMPAGLIFLOZIN or the DPP-4 inhibitor at end of study
- Proportion of subjects who discontinued EMPAGLIFLOZIN or the DPP-4 inhibitor before end of study
- Proportion of subjects still on EMPAGLIFLOZIN or the DPP-4 inhibitor at end of study or who discontinued EMPAGLIFLOZIN or the DPP-4 inhibitor no more than 30 days before end of study
- Proportion of subjects who discontinued EMPAGLIFLOZIN or the DPP-4 inhibitor 31 to 120 days before end of study
- Proportion of subjects who discontinued EMPAGLIFLOZIN or the DPP-4 inhibitor more than 120 days before end of study

The exposure parameters will be described by frequency and summary tables by group. Duration of treatment and extent of exposure will be evaluated as continuous count of number of days and in categories of 1 to 30 days, 31 to 90 days, 91 to 180 days, 181 to 360 days and more than 360 days, respectively.

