8.2 SECONDARY OBJECTIVE

To estimate the risk of each primary outcome with respect to the following definition of exposure:

- The Ramadan period

(1st day of Ramadan to 29th day of Ramadan based on the Islamic Hijri calendar)

[figure not shown]

Figure 1: Ramadan period during study follow-up time

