- Concomitant medications including new medications taken since last visit: any change in the concomitant medications (dose and dosing intervals)
- Any adverse events noted
- Study completion status
- Discontinuation or continuation (if interruption, date of last administration, reason for interruption)
- PASS physician's electronic signature for data integrity

9.2.2.3 Visit 3; 32±2 weeks from Visit 1

After 32±2 weeks from Visit 1, the patients will return for follow-up. The followings will be noted and recorded in the e-CRF.

- Visit date
- Physical examination: blood pressure, pulse rate, weight (if available)
- HbA1C (if available)
- Any change of Empagliflozin or comparator DPP-4 inhibitor given
- Concomitant anti-hyperglycaemic agent including new medications taken since last visit: any change in the concomitant medications (dose and dosing intervals)
- Concomitant medications including new medications taken since last visit: any change in the concomitant medications (dose and dosing intervals)
- Any adverse events noted
- Study completion status
- Discontinuation or continuation (if interruption, date of last administration, reason for interruption)
- PASS physician's electronic signature for data integrity

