9.7.2 Main analysis using stratification

For the incident users of Empagliflozin along with their respective comparators, analysis will be performed using the “as-treated” (AT) approach. This corresponds to censoring individuals who discontinue use of the index drug, i.e. who either switch from the index drug to any other of the index drugs (Empagliflozin or DPP-4 inhibitor) during follow-up or who stop using the index drug. The AT approach is considering index periods.

For each event of interest, ketoacidosis, severe urinary tract infections, volume depletion, and dehydration, crude and adjusted incidence rates per cohort will be described and compared by means of incidence rate ratios (IRR). Incidence rates will be reported as point estimates and 95% confidence intervals (CIs). Crude incidence rates will be adjusted per 1,000 person-years. Per cohort and, where appropriate per stratum and/or subgroup, the number of person-years is the sum of length of index periods of all patients. Time to first event occurrence will be compared by means of hazard ratios and their 95% confidence intervals.

IRRs and hazard ratios are analysed using stratification. Strata are defined by PS quintiles. IRRs are investigated by means of a stratified Mantel-Haenszel analysis, while hazard ratios are investigated by means of a Cox regression, if proportional hazards can be assumed.

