4.7.5 Ketoacidosis, severe UTI, depletion and dehydration

As main endpoints, ketoacidosis, severe UTI (namely pyelonephritis and urosepsis), volume depletion and dehydration, will be derived from corresponding AE reporting. Crude and treatment-adjusted incidence rates will be presented by group and period, together with incidence rate ratios of EMPAGLIFLOZIN relative to DPP-4 inhibitor, as point estimates and with 95% confidence limits. Treatment-adjusted incidence rates are defined as crude incidence rates per 1,000 person-years. Per group, and, where appropriate, per stratum and/or subgroup, the number of person-years is the sum of length of index periods of all respective patients.

For each endpoint, the time from index date to first occurrence in days is determined. If the endpoint does not occur for a patient, the time is right-censored by the duration of the respective period, index period or follow-up period. By group, times to first occurrence will be described by means of Kaplan-Meier estimates with 95% confidence limits and, where appropriate, median times with 95% confidence limits.

Crude and treatment-adjusted incidence rates and respective incidence rate ratios will be described in summary tables by group and period, and per period in subgroups by metformin status, GLD status and insulin status, respectively. Ratios are defined as Empagliflozin to DPP-4 inhibitors.

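### As-treated person-time includes interruption days and ends differently in the SAP and the protocol; the effect is small over 12 months but can be material in the Ramadan analysis

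*SAP*

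**What the plan says.** **SAP.** Section 4.4 runs the index period from the index date to the end of treatment and mentions neither gaps nor a grace period. Section 4.7.3 lists "Duration of treatment as the length of the index period in days" and then, as a separate parameter, "Extent of exposure as duration of treatment minus the number of days with interruptions". Both appear only in descriptive exposure tables. For the four outcomes, section 4.7.5 states that "the number of person-years is the sum of length of index periods of all respective patients", and it censors time to first event at the end of the same period. Section 4.9.2 analyses the Ramadan endpoints in the same way, on the part of the index period that falls in Ramadan.

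**Protocol.** Section 9.7.2 uses the same denominator: "the number of person-years is the sum of length of index periods of all patients". Section 9.7, however, ties the index period to current use, which section 9.3.2 runs "to the end of supply for that prescription plus a period of 30 days". The next 90 days are classed as recent use. Section 9.3.2 adds: "Discontinuation of the index drug will be defined as no further prescription 120 or more days after the end of the last" prescription's supply. Section 8.2 defines the Ramadan period as "1st day of Ramadan to 29th day of Ramadan based on the Islamic Hijri calendar".

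**Data items.** The protocol's lists for Visits 2 to 4 ask for: "Discontinuation or continuation (if interruption, date of last administration, reason for interruption"). They name no restart date.

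**The concern.** The main analysis is called as-treated, yet the SAP keeps days off the drug in the exposed denominator and in the time at risk. The two documents also share the name index period but not its end, so two programmers could produce different primary rates from the same data.

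The stakes are highest for Ramadan. The regulator asked for that period, it is short, and one pause can fill it. If the drug raises risk and its users pause more often than comparator users, counting paused days as exposed pulls the rate ratio towards no difference. In a safety study that is the unwelcome direction.

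**Working it through.** There is no sample-size or power figure to reproduce here; the 1,500 patients are a regulator's requirement. The check compares definitions, counts calendar days and then works through an illustrative dilution.

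**1. Are interruption days in the denominator?** Person-years are the sum of index-period lengths (SAP 4.7.5). Index-period length is the duration of treatment, and extent of exposure is that duration minus interruption days (SAP 4.7.3). Interruption days therefore lie inside the index period and stay in the denominator. For a 365-day index period with a 29-day pause:
- extent of exposure: 365 − 29 = 336 days
- paused share: 29/365 = 7.9%
- if all events fell on drug, that patient's rate would rise by 365/336 = 1.086 on interruption-free time.

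**2. A gap longer than 30 days, then resumption.** Take supply ending on day 180, a restart after more than 30 days, and treatment to day 365.
- SAP 4.4: 365 days.
- Protocol, with current use ending at the gap: 180 + 30 = 210 days.
- If a new prescription were read as reopening current use, the protocol would drop only the gap days beyond 30. That still differs from the SAP.

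**3. Length of Ramadan against the 30-day grace.**
- Protocol 8.2: 29 days.
- SAP Table 2-1, 5 May to 4 June 2019: 27 + 4 = 31 days inclusive; 23 April to 23 May 2020: 8 + 23 = 31.
- SAP 4.4 end dates of 6 June 2019 and 25 May 2020, from the Table 2-1 starts: 27 + 6 = 33 and 8 + 25 = 33.

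Consider a patient who pauses for the whole period and later resumes. Under the SAP all 29 or 33 days count as exposed. Under the protocol, with supply ending the day before Ramadan, all 29 days count, or 30 of the 33 (33 − 30 = 3 fall outside). The grace runs from end of supply, so tablets left over extend the counted time further.

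**4. Illustrative dilution.** Assume a share q of empagliflozin users pauses for 29 days, no comparator user pauses, and the off-drug rate equals the comparator rate. With w the off-drug share of empagliflozin person-time and T the true rate ratio:

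observed ratio = T(1 − w) + w

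Here w = q for a 29-day Ramadan, q × 29/33 for the 33-day window, and q × 29/365 for 12 months.

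| T | q | Ramadan, 29 days | Ramadan, 33 days | 12 months |
|---|---|---|---|---|
| 3 | 0.10 | 2.80 | 2.82 | 2.98 |
| 3 | 0.25 | 2.50 | 2.56 | 2.96 |
| 3 | 0.50 | 2.00 | 2.12 | 2.92 |
| 2 | 0.10 | 1.90 | 1.91 | 1.99 |
| 2 | 0.25 | 1.75 | 1.78 | 1.98 |
| 2 | 0.50 | 1.50 | 1.56 | 1.96 |

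Example: T = 3, q = 0.50, 33 days: w = 0.50 × 29/33 = 0.439, and 3 × 0.561 + 0.439 = 2.12. With T = 1 the observed ratio is 1 for any q.

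**The case against.** The strongest reply is that keeping short gaps under a grace period is a usual as-treated convention, and that the stated aim is safety in real-life use, Ramadan included. Restricting the Ramadan estimate to on-drug days would also condition on behaviour after baseline. Patients who stop because symptoms have begun would have their events moved out of the exposed row, which could hide a signal. This stands, and it is why the index-period estimate should remain and the on-drug analysis be added beside it.

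SAP section 3 does carry the 30-day grace. It does so as a rule for ending follow-up, and SAP 4.4 does not use it to define the index period. The reply narrows the mismatch for long gaps only if section 3 is read as overriding 4.4, which neither section says.

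A reader might also infer more than the documents support:
- *That gaps of 31 to 119 days are undefined, so up to a third of a year off drug (119/365 = 33%) enters the main analysis by protocol.* Section 9.3.2 names that interval recent use, and section 9.7 ties the index period to current use. The protocol's operative limit is 30 days.
- *That Ramadan is always shorter than the grace.* This is true of the 29-day definition, not of the SAP's 33-day window.
- *That 30% pausing on empagliflozin against 10% on comparator multiplies the ratio by 0.70/0.90 = 0.78.* This needs no events at all off drug, although these outcomes have a background risk. With the off-drug rate equal to the comparator's, a true ratio of 2 is multiplied by (0.7 × 2 + 0.3)/2 = 0.85, and a true ratio of 1 is unchanged.
- *That interruption days cannot be derived.* The e-CRF is not among the documents. Protocol 9.10.2.1 lists visit dates with prescription of study medication as source data, and the SAP plans listings of treatment details and continuation status.
- *That no on-drug analysis is planned.* The protocol abstract promises sensitivity analyses for alternative definitions of exposure, and SAP 4.9.3 is not in the public text. A sensitivity analysis there would still not reconcile the primary definitions.

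**Conclusion.** The point holds on the text. The SAP counts interruption days as exposed in the primary and Ramadan rates, and the end of the index period differs between SAP 4.4 and protocol 9.7/9.3.2. For the 12-month analysis a single 29-day pause matters little, and no material bias is shown there. For Ramadan, a true ratio of 3 could be reported as anything from 2.80 down to 2.00 over 29 days, or from 2.82 down to 2.12 over 33 days. These sizes rest on assumed pausing shares of 10% to 50% in the empagliflozin group alone and on an off-drug rate equal to the comparator's; the documents give neither. The direction could differ if comparator users also pause and risk off drug is not the comparator's.

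**What to change.** 1. Use one index-period definition in SAP 4.4 and 4.7.5 and protocol 9.3.2 and 9.7. Carry the protocol's 30-day current-use limit into the SAP, say what happens to person-time when a patient resumes after a longer gap, and state that recent use and the 120-day category do not extend as-treated person-time.
2. Keep the index-period estimate. Add, for the primary tables and especially the Ramadan tables, a sensitivity analysis on interruption-free person-time, using the extent of exposure that the SAP already plans to derive. Show events and days on drug and paused in separate rows.
3. Confirm that the e-CRF captures a restart date. If it does not, add one to the interruption item at Visits 2 to 4.

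The cost is wording, one set of extra tables and possibly one date field. The sensitivity analysis has a little less person-time, and some events after symptom-driven stopping will fall in the paused row. Restart dates for pauses before the amendment, including Ramadan 2019, may need site queries, and an amendment needs ethics and authority approval.
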